##### **3.1.2. Full Analysis Set**

The Full Analysis Set (FAS) includes all subjects who were either randomized or enrolled into the study, and received at least 1 dose of study drug. The study drugs in this study are LDV/SOF and SOF+RBV for Cohort 1 and LDV/SOF for Cohort 2. For Cohort 1, subjects are grouped within the FAS by the treatment group to which they were randomized.

This is the primary analysis set for efficacy analyses.

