### **3.4. Examination of Subject Subsets**

Subsetting of subjects based on randomization stratification factors will be explored for subgroup analyses. If there are discrepancies in stratification factor values between the IWRS and the clinical database, the values recorded in the clinical database will be used for analyses.

Other subject subsets will also be explored for the primary efficacy endpoint (SVR12), including the following:

- age (< 65 years,  $\geq$  65 years)
- sex (male, female)
- baseline BMI ( $< 25 \text{ kg/m}^2$ ,  $\geq 25 \text{ kg/m}^2$ )
- HCV genotype subtype (if applicable)
- cirrhosis (cirrhosis, absence of cirrhosis, missing)

- IL28B (CC, non-CC; with non-CC further broken down to CT, TT)
- Baseline HCV RNA (< 800,000 IU/mL,  $\geq$  800,000 IU/mL, and  $< 5 \log_{10}$  IU/mL,  $\geq 5 \log_{10}$  IU/mL)
- baseline alanine aminotransferase (ALT) ( $\leq 1.5 \times$  upper limit of normal [ULN],  $> 1.5 \times$  ULN)
- prior HCV treatment experience (treatment naive, treatment-experienced)
- most recent prior HCV treatment response (non-responder, relapse/breakthrough, early treatment discontinuation, met a virologic stopping rule, not otherwise listed, unknown) for treatment-experienced subjects
- completed study treatment, discontinued study treatment
- adherence to study regimen (<80%,  $\geq$  80%)

The primary efficacy endpoint for Cohort 2 will be examined using the applicable subsets above.

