### **3.6. Missing Data and Outliers**

#### **3.6.1. Missing Data**

In general, missing data will not be imputed unless methods for handling missing data are specified.

For missing last dosing date of study drug, imputation rules are described in Section 3.8.1. The handling of missing or incomplete dates for adverse event (AE) onset is described in Section 7.1.5.2, and for prior and concomitant medications in Section 7.4.

For analyses of categorical HCV RNA data, missing posttreatment HCV RNA data will have the missing data imputed. Missing on-treatment HCV RNA will have the missing data imputed up to the time of the last dose (for on-treatment displays). If the study day associated with the last dosing date is greater than or equal to the lower bound of a visit window, and the value at the visit is missing, the value will be imputed. If the study day associated with the last dosing date is less than the lower bound of a visit window then the on-treatment value at that visit will remain missing.

If an HCV RNA data point is missing and is preceded and followed in time by values that are “< lower limit of quantitation (LLOQ) target not detected (TND)”, then the missing data point will be set to “< LLOQ TND”. If a data point is missing and preceded and followed by values

that are “< LLOQ detected”, or preceded by “< LLOQ detected” and followed by “< LLOQ TND”, or preceded by “< LLOQ TND” and followed by “< LLOQ detected”, then the missing value will be set to “< LLOQ detected”. In these situations the data point will be termed a bracketed success; otherwise, the data point will be termed a bracketed failure (ie,  $\geq$  LLOQ detected). If a data point is missing and is not bracketed, the missing data point will also be termed a failure (ie,  $\geq$  LLOQ detected) except for SVR24, which will be imputed according to SVR12 status. Success for SVR12 who have no further HCV RNA measurements collected will be counted as a success for SVR24 due to the high correlation between these 2 endpoints.

For the analyses of continuous HCV RNA efficacy data, when and only when a missing HCV RNA value is imputed as < LLOQ TND or < LLOQ detected according to the imputation rule described above, the corresponding continuous value will be imputed to LLOQ - 1 IU/mL. No other imputation will be performed for continuous HCV RNA data.

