**Table 3-2. Analysis Windows for Posttreatment HCV RNA, Vital Signs and Safety Laboratory Data**

Nominal FU a Visit	HCV RNA			Vital Signs and Safety Laboratory Data b		
	Nominal FU Day	Lower Limit	Upper Limit	Nominal FU Day	Lower Limit	Upper Limit
FU-4	28	21	69	28	4	30
FU-12	84	70	146	NA	NA	NA
FU-24	168	147	210	NA	NA	NA

a FU-x visit = posttreatment Week-x follow-up visit.

b Vital signs and safety labs will only be summarized for the FU-4 visit (up to 30 days after last dose).

ECG data collected up to the last dose date + 3 days are considered to be on-treatment data. Qualitative assessments of whether the ECG is normal or abnormal will be assessed for on-treatment data based on the visit windows as shown in Table 3-3.

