- Who had HCV posttreatment Week 4 assessment but no HCV posttreatment Week 12 assessment and thereafter (With HCV FU-4 but No FU-12 and thereafter)

If a subject did not have any HCV RNA assessment  $\geq$  21 days after the last dose of any study drug (ie, lower bound of FU-4 visit for HCV RNA data), the subject is categorized as having “No HCV FU-4 and thereafter”. If a subject had the HCV FU-4 assessment but did not have any HCV RNA assessment  $\geq$  70 days after the last dose of any study drug (ie, lower bound of FU-12 visit for HCV RNA data), the subject is categorized as having “With HCV FU-4 but No FU-12 and thereafter”.

In addition, the total number of subjects who were randomized, and the number of subjects in each of the disposition categories listed above will be depicted by a flowchart.

The following by-subject listings will be provided by subject ID number in ascending order to support the above summary tables:

- Disposition for subjects who complete study treatment and study
- Disposition for subjects who did not complete study treatment and/or study with reasons for premature discontinuation of study treatment and/or study
- Lot number and kit ID (if applicable)

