#### 6.1.3. Primary Analysis of the Primary Efficacy Endpoint

In Cohort 1, the primary analyses will consist of a non-inferiority (delta=10%) of LDV/SOF for 12 weeks to SOF+RBV for 12 weeks at the 0.05 significance level (two-sided). Non-inferiority will be demonstrated (ie, non-inferiority null hypothesis will be rejected) if the lower bound of the two-sided 95% CI for the difference ( $P_1 - P_2$ ) in SVR12 is greater than -10%.

The two-sided 95% CI on the difference in SVR12 rates between the 2 treatment groups will be constructed based on stratum-adjusted MH proportions for the assessment of non-inferiority as follows {Koch 1989}:

$$P_1 - P_2 \pm Z_{(1-\alpha/2)} * SE(P_1 - P_2),$$

where

- $(P_1 - P_2) = \frac{\sum w_h d_h}{\sum w_h}$ , is the stratum-adjusted MH proportion difference, where  $d_h = p_{1h} - p_{2h}$  is the difference in the proportion of SVR12 of Treatment Groups 1 and Treatment Group 2 in stratum h (h=1 and 2).
- $w_h = \frac{n_{1h} n_{2h}}{n_{1h} + n_{2h}}$ , is the weight based on the harmonic mean of sample size per treatment group for each stratum where  $n_{1h}$  and  $n_{2h}$  are the sample sizes of Treatment Groups 1 and 2 in stratum h.
- $SE(P_1 - P_2) = \sqrt{\frac{\sum w_h^2 \left[ \frac{p_{1h}^*(1-p_{1h}^*)}{n_{1h}-1} + \frac{p_{2h}^*(1-p_{2h}^*)}{n_{2h}-1} \right]}{(\sum w_h)^2}}$ , where  $p_{1h}^* = \frac{m_{1h} + 0.5}{n_{1h} + 1}$  and  $p_{2h}^* = \frac{m_{2h} + 0.5}{n_{2h} + 1}$  and  $m_{1h}$  and  $m_{2h}$  are the number of SVR12 in Treatment Groups 1 and 2 in stratum h.
- $\alpha = 0.05$  for this study
- $Z_{(1-\alpha/2)} = Z_{0.975} = 1.96$  is the 97.5th percentile of the normal distribution

If the computed lower confidence bound is less than -1, the lower bound is defined as -1. If the computed upper confidence bound is greater than 1, then the upper bound is defined as 1.

The two-sided 95% exact CI based on binomial distribution (Clopper-Pearson method) will be provided for the SVR12 rate for each treatment group in Cohort 1 {Clopper 1934}.

In the primary efficacy analysis of Cohort 2, the SVR12 rate will be calculated along with two-sided 95% exact CI using Clopper-Pearson method.

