#### 6.1.4. Subgroup Analysis of the Primary Efficacy Endpoint

Point estimates and 95% exact CIs of the SVR12 rates for each treatment group in each cohort, and of the difference (Group 1 – Group 2) in SVR12 rates will be displayed for each subgroup outlined in Section 3.4 for cohort 1.

The two-sided 95% exact CI based on Clopper-Pearson method will be provided for the SVR12 rate within each treatment group and subgroup. CIs on the difference of SVR12 rates within each subgroup will be constructed based on the standardized statistic and inverting two 1-sided tests {Chan 1999}.

A Forest Plot will graphically present point estimates and the two-sided 95% exact CIs on the treatment differences (Group 1 – Group 2) in SVR12 rates for each of the subgroups for Cohort 1.

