## 6.2.2. Analysis Methods for Secondary Efficacy Endpoints

For analyses of HCV RNA < LLOQ by visit while on treatment and during the posttreatment (SVR) follow-up period, subjects will be assigned a value at each visit based on the analysis visit windows specified in Section 3.8.2. Missing values will be imputed based on the categorical imputation rules described in Section 3.6.1. The two-sided 95% exact confidence interval based on Clopper-Pearson method will be provided for the percentage of subjects with HCV RNA < LLOQ at each visit in each treatment group. The overall category for “HCV RNA < LLOQ” will be split into the following 2 subcategories: “< LLOQ TND” for subjects with target not detected and “< LLOQ detected” for subjects with < LLOQ detected in tabular displays.

Graphs for the percentage of subjects with HCV RNA < LLOQ over time during treatment will be displayed.

Summary statistics will be presented for absolute values and change from baseline in HCV RNA ( $\log_{10}$  IU/mL) by visit through EOT. Imputation rules described in Section 3.6.1 will be used to assign HCV RNA values for missing values at a visit that are bracketed by “< LLOQ TND” and/or “< LLOQ detected”. Otherwise, a missing = excluded analysis will be performed. Plots of the mean  $\pm$  SD and median (Q1, Q3) of absolute values and changes from baseline in HCV RNA through EOT will be presented.

[figure not shown]
For the SVR12 endpoint analysis, a summary table of the number and percentage of subjects with SVR12, virologic failure (VF), and Other will be created. All subjects who achieve SVR12 will be categorized as SVR12. Virologic failure will be descriptively summarized as “on-treatment virologic failure” and relapse (which will be broken down by study drug completed yes/no). Subjects who do not achieve SVR12 and do not meet criteria for VF will be categorized as “Other”. The denominator for relapse will be the number of subjects who had HCV RNA < LLOQ on their last observed on-treatment HCV RNA measurement; otherwise, the denominator will be the number of subjects in the FAS.

A concordance table between SVR12 and SVR24 will be provided for each treatment group in each cohort. Subjects with both observed SVR12 and observed SVR24 data will be included for this analysis.

Drug resistant substitutions will be analyzed as part of the Virology Study Report.

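### Does the Cohort 1 non-inferiority conclusion need a second, pre-specified rule for missing SVR12?

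*SAP*

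**What the plan says.** SAP 3.6.1 and Protocol 8.3 give the same rule. A missing post-treatment HCV RNA value lying between two results below LLOQ is a success. Otherwise, "If a data point is missing and is not bracketed, the missing data point will also be termed a failure"; SVR24, which follows SVR12, is the only exception.

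The rule is applied in the FAS (SAP 3.1.2: "This is the primary analysis set for efficacy analyses"). SAP 6.1.3 states the decision: "Non-inferiority will be demonstrated (ie, non-inferiority null hypothesis will be rejected) if the lower bound of the two-sided 95% CI" for the difference, LDV/SOF minus SOF+RBV, lies above -10%. The interval uses Mantel-Haenszel weights over the randomization strata.

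Four other parts of the SAP bear on missing outcomes:

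- **SAP 4.1** counts, among treatment completers and among discontinuers, those with no HCV RNA from FU-4 onward and those lost between FU-4 and FU-12 (the definition begins "If a subject had the HCV FU-4 assessment but did not have any HCV RNA assessment").
- **SAP 6.2.2** splits the outcome into SVR12, virologic failure and a residual class ("Subjects who do not achieve SVR12 and do not meet criteria for VF will be categorized as" Other).
- **SAP 3.4** lists "completed study treatment, discontinued study treatment" and adherence as subgroups, and 6.1.4 gives each a between-arm interval: "CIs on the difference of SVR12 rates within each subgroup will be constructed based on the standardized statistic and inverting two 1-sided tests".
- **Table 3-2** ("Analysis Windows for Posttreatment HCV RNA, Vital Signs and Safety Laboratory Data") accepts any HCV RNA value from day 70 to day 146 as FU-12.

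**The concern.** Counting a missing outcome as failure is cautious for a single response rate. It is not automatically cautious for a non-inferiority difference. Each missing control outcome lowers P2 and moves the difference toward LDV/SOF; each missing LDV/SOF outcome does the opposite. The trial is open-label, and Protocol 7.5.2 ties permanent ribavirin discontinuation to stopping sofosbuvir, so unequal early stopping is conceivable.

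The SAP defines no per-protocol or observed-case set. Its only statement about sensitivity analyses (3.6.2) declines them for outliers. A reader could therefore fear that a result near -10% turns on one or two subjects with no FU-12 sample, and that nothing planned in advance would say so.

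**Working it through.** **1. The plan's own figure.** Inputs from SAP 1.3: 100 per arm, 96% in both, margin 10 points, one-sided 0.025. The unpooled SE is sqrt(2 × 0.96 × 0.04 / 100) = 0.0277. Then 0.10/0.0277 - 1.96 = 1.65, so power is 95.0%. Exact enumeration with the 6.1.3 standard error in one stratum gives 92.5%; a continuity correction gives 90.1%. All agree with the stated power of over 90%. Under assumed strata of 45/45/5/5 per arm the figure is 89.1% with nothing missing, so that drop comes from the small strata.

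**2. What the planned test targets.** Under 3.6.1 a subject without an outcome is a non-responder, so the rule is part of the endpoint. Take response of 86% and 96% among those observed, with 2% missing in the control arm only:

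- P2 = 0.96 × 0.98 = 0.9408
- P1 - P2 = 0.86 - 0.9408 = -0.0808

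That is inside the margin, so declaring non-inferiority there is not a false positive on the planned endpoint. At that endpoint's own boundary (84.08% versus 94.08%), exact enumeration in one stratum gives 2.7%. At 86% versus 96% with nothing missing it gives 2.9%. The planned test's error rate is not inflated.

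**3. Against the other target: response had nobody been missing.** Simulation of the 6.1.3 interval at 86% versus 96%, strata 45/45/5/5, missingness unrelated to outcome. The repeat leaves out subjects with a missing outcome.

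| Missing LDV/SOF | Missing SOF+RBV | Planned analysis | Repeat |
|---|---|---|---|
| 0 | 0 | 2.2% | 2.2% |
| 2% | 2% | 2.5% | 2.2% |
| 2% | 0 | 0.8% | 2.2% |
| 3.8% | 0 | 0.3% | 2.2% |
| 0 | 2% | 5.8% | 2.2% |
| 0 | 2.6% | 7.4% | 2.1% |

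Only the control-only rows exceed 2.5%.

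**4. Which row the documents support.** Protocol 1.2.2.2 accounts for all 140 subjects on SOF+RBV: 135 with SVR12 plus 5 relapses, so 0 missing. Protocol 1.2.2.4 has one loss among 26 on LDV/SOF for 12 weeks: 1/26 = 3.8%. Taken at face value, that is the fourth row. There the rule makes non-inferiority harder to show, and no simulated trial met -10% in the planned analysis and missed it in the repeat. The 2.6% in the last row is the upper exact 95% limit for zero events, 1 - 0.025^(1/140). The evidence is thin (the exact interval for 1/26 is 0.1% to 19.6%), but it gives no support to control-only missingness.

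**5. Near the margin.** One stratum, 6.1.3 standard error, assumed counts:

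- LDV/SOF 92/100, control 94/100 with 2 of the 6 non-responders missing: lower bound -2.0 - 1.96 × 3.72 = -9.3%.
- Control 94/98 after leaving those 2 out: -3.9 - 1.96 × 3.50 = -10.8%. The decision changes.
- LDV/SOF 91/100, control 94/100, nothing left out: -3.0 - 1.96 × 3.83 = -10.5%. One ordinary additional failure also changes it.
- 4 virologic failures and 2 missing in each arm: -6.8% as planned, -5.9% observed only, -8.3% with missing as failure on LDV/SOF and success on control. All meet -10%.

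Sensitivity to one or two outcomes at the boundary is a property of 100 per arm, not of this missing-data rule.

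**6. What a repeat would do at the design rates.** With 96% in both arms and 1.25% missing in each, strata 45/45/5/5, the planned analysis alone meets -10% in 1.8% of trials and the repeat alone in 7.7%. The repeat would more often rescue a failed primary than question a successful one.

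**The case for a change.** The strongest case for the concern is that none of the planned tables yields the 6.1.3 lower bound under a different rule. The completer and adherence subgroups keep missing as failure, are not stratum-adjusted, and split on treatment completion or adherence rather than on whether an FU-12 value exists. A pre-specified repeat would cost one sentence and one table row, and would remove any choice made after the results are known in an open-label trial.

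All of that is correct as description, and a sponsor could reasonably add the row. It does not show that the plan is wrong. The repeat would leave the decision where it is. It selects subjects on an event after randomization and gives no protection when missingness is related to outcome, so it is not a better method than the planned one. The SAP 4.1 and 6.2.2 counts, reported by arm, let a reader see how many failures come from missing data and approximate an unstratified repeat. The completer subgroup already carries a between-arm interval from which the kind of loss seen in the earlier LDV/SOF study, a withdrawal before treatment completion, would be absent. Finally, SAP 6.3 is redacted, so the absence of a further analysis cannot be established.

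**Conclusion.** The concern does not hold. One missing-data rule is stated identically in protocol and SAP and applied in the FAS with one decision bound. The error rate on that endpoint stays near its nominal level (2.7% to 2.9% in one stratum, against 2.5%). The larger figures, 5.8% and 7.4%, need missing outcomes in the control arm only and refer to a quantity the SAP does not test. With equal missingness of 2% the figure is 2.5%, and with the losses seen in the earlier studies it is 0.3%.

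Few missing outcomes are to be expected: the FU-12 window is wide, bracketed values are recovered, and Protocol 3.4 asks for follow-up to continue after early stopping. The documents give no missing-data rate or stratum sizes for this trial, so the simulated figures rest on assumed missing shares, strata of 45/45/5/5 and missingness unrelated to outcome. The verdict on the plan does not depend on those assumptions, because it rests on the rule, the analysis set and the decision bound being fixed and consistent. What remains is a preference for one more supportive row.

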### **3.6.2. Outliers**

Outliers will be identified during the data management and data analysis process, but no sensitivity analyses will be conducted. All data will be included in the data analysis.

### **3.7. Data Handling Conventions and Transformations**

By-subject listings will be presented for all subjects in the Safety Analysis Set and sorted by subject ID number, visit date, and time (if applicable) unless otherwise specified. Data collected on log forms, such as AEs, will be presented in chronological order for each subject.

Age (in years) on the date of the first dose of study drug and sex at birth will be used for analyses and presentation in listings.

If a subject was not dosed with study drug at all, then the date the informed consent was signed will be used instead of first dose date of study drug. For some countries, only birth year is collected on the case report form (CRF). In those cases, “01 January” will be used for the unknown birth day and month for the purpose of age calculation, unless age is captured on the CRF.

Data that are continuous in nature but are less than the lower limit of quantitation or above the upper limit of quantitation will be imputed as follows:

- A value that is one unit less than the limit of quantitation will be used for calculation of descriptive statistics if the datum is reported in the form of “ $< x$ ” (where  $x$  is considered the limit of quantitation). For example, if the values are reported as  $< 50$  and  $< 5.0$ , values of 49 and 4.9, respectively, will be used for calculation of summary statistics. An exception for this rule is any value reported  $< 1$ . For the values reported as  $< 1$  or  $< 0.1$ , value of 0.9 or 0.09 will be used for calculation of summary statistics.
- A value that is one unit above the limit of quantitation will be used for calculation of descriptive statistics if the datum is reported in the form of “ $> x$ ” (where  $x$  is considered the limit of quantitation). Values with decimal points will follow the same logic as above.
- The limit of quantitation will be used for calculation of descriptive statistics if the datum is reported in the form of “ $\leq x$ ” or “ $\geq x$ ” (where  $x$  is considered the limit of quantitation).

The COBAS® AmpliPrep/COBAS® TaqMan® HCV Quantitative Test, v2.0 was used to determine HCV RNA results in this study. The LLOQ of the assay is 15 IU/mL.

When the calculated HCV RNA value is within the linear range of the assay, then the result will be reported as the “ $<<$  numeric value $>>$  IU/mL”. This result will be referred to in this document as the numeric result or as “ $\geq$  LLOQ detected” for categorical result.

When HCV RNA is not detected, the result is reported as “No HCV RNA detected” or “target not detected”. This result will be referred to in this document as “ $<$  LLOQ target not detected” or “ $<$  LLOQ TND”.

When the HCV RNA IU/mL is less than LLOQ of the assay, the result is reported as “ $< 15$  IU/mL HCV RNA detected”. This result will be referred to in this document as “ $<$  LLOQ detected”.

The overall category of HCV RNA  $<$  LLOQ includes “ $<$  LLOQ TND” and “ $<$  LLOQ detected.” For numerical HCV RNA data, values below LLOQ will be set to the LLOQ – 1 IU/mL (ie, 14 HCV RNA IU/mL). HCV RNA values returned as “target not detected” will also be set to 14 IU/mL.

For selected analyses, HCV RNA data (IU/mL) will be transformed to the logarithmic (base 10) scale ( $\log_{10}$  IU/mL).

### **3.8. Visit Windows**

#### **3.8.1. Definition of Study Day**

Study day is the day relative to the date of the first dose of study drug. Study Day 1 will be defined as the day of first dose of study drug administration.

Study day will be calculated from the date of first dose of study drug administration and derived as follows:

- For postdose study days: Assessment Date – First Dose Date + 1
- For days prior to the first dose: Assessment Date – First Dose Date

The last dose date for an individual study drug will be the end date on study drug administration eCRF for the record where the “subject permanently discontinued” flag is ‘Yes’. The last dose date will be defined as the maximum of the last dose dates of individual study drugs in a treatment group.

If there are subjects for whom the date of last study drug is unknown due to the reason that the subject was lost to follow-up and not able to be contacted, the date of last dose will be estimated using the maximum of nonmissing study drug start or stop dates, visit dates and laboratory collection dates (posttreatment visits and unscheduled visits are not included).

